We determined sample size of 10 subjects based on published neuroimaging studies [111, 186]. The fMRI meditation study of Lazar et.al. [143] reported significant results with five subjects. Two PET studies of meditation [142, 144] reported significant signal changes with nine and four subjects, respectively. Litscher's recent study of Qigong [187] examined cerebral blood flow using two subjects, but reported no estimates of significance. Newberg et.al. [73] neural SPECT study of Tibetan meditation reported significant blood flow changes with eight subjects. An examination of 50 reports on PET or fMRI imaging of hypnosis, acupuncture, complex cognitive tasks, or simple sensory and motor stimulation showed that statistical significance was found with 10 or less subjects [see for example, 108, 111, 162, 188, 189-199].

D.5. Examine the Patterns of Neural Activity during the De-Excitation Substate (Aim 1).

Experiment 1: Selection of epoch length and control condition to image the de-excitation process.

D.5.1. Hypotheses. We will be testing two hypotheses in this experiment.**D.5.1.1 Epoch length.** We hypothesize that the shorter epoch length in a ABC-cycling protocol (randomly-ordered meditation and controls) will best 'frame' the initial de-excitation process due to significantly higher signal-to-noise ratio, higher signal intensity and less variance in the statistical test;

D.5.1.2. Control conditions. We hypothesize significant differences in signal intensity across the three different epoch conditions—TM, passive-attending and mental-counting, including in rank order: de-excitation will be maximum for TM, then passive-attending, and lastly, mental-counting.

D.5.2. Issues.

D.5.2.1. Epoch length. Epoch length will be pre-framed during our subject selection protocol. We will examine two epoch lengths centered on this preliminary value. The best frame will include maximum duration of the de-excitation process without the actual onset of a SBQ for most of the meditation epochs.

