We will record fMRI (in first 10 subjects meeting inclusion criteria) during randomly ordered epochs of controls and TM practice. We will use two cycling ABC-run with eyes-closed. Each ABC-run comprises TM and two control conditions: (1) listening passively to nature (ie, ocean) sounds or (2) mental-counting by '2s'. An ABC-run (for example, using 30 sec epochs) will last about 22min, including 45 total epochs, 15 epochs each condition. This will result in 22 min/run x two epoch lengths = 45 min of testing, plus 40 min of preliminary anatomic scans, for a total time of less than 2 hr per MRI session. Whole-brain scans will be recorded from 19 slices per scan. At the end of each 22-min run, subjects will be asked to report their experiences. Carryover effects will be minimized by: (1) inserting one minutes breaks between runs. During these breaks we will be speaking and de-briefing the subjects; and (2) randomly presented control conditions in the same run. With this design, *within*-sets comparison will provide an estimate of the *minimal* carryover effects and *across*-sets will provide an estimate of *maximal* carryover effects.

D.5.4. Analysis for Hypotheses 1 & 2.

The data will be processed, and clusters of significant fluctuations in signal intensity will be noted (see Sect. D.2.2-D.2.3.). We expect clusters of fluctuations in signal intensity in 4-8 brain areas (see Sect. B.). The Z-statistics for areas of significant fluctuations in signal intensity will be noted from all runs and used as the variate in a repeated measures MANOVA. In this MANOVA, brain areas (4-8 estimate), and epoch condition (3) will be the factors, and the epoch-lengths (2) will be the repeated measure. For all main effects, individual comparisons will be conducted.

1. We expect **main effects for brain areas**, indicating significant differences in signal intensity between one or more brain areas. These changes may include in rank order: basal forebrain increases, slight cerebral and cerebellar cortex and mesencephalic reticular formation decreases, and no decreases in medial thalamus.
2. We expect **main effects for epoch condition**, indicating significant differences in signal intensity across the three different conditions—TM, passive-attending and mental-counting. These changes may include in rank order: de-excitation will be maximum for TM, then passive-attending, and lastly, mental-counting.

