3. We expect **main effects for the repeated measures**, indicating the epoch length that best framed the initial de-excitation of TM practice. For example, longer epoch lengths run the risk of introducing new, and variable cognitive and brain processes. This variability could result in lower signal-to-noise ratio, low signal intensity and more variance in the statistical test.
4. We expect **significant epoch length x epoch condition interactions**. We expect less cognitive and brain variability in the shorter epoch length regardless of condition resulting in greater distinction between epoch conditions. On the other hand, the greater variability of the longer epoch length may diminish the measured difference in signal intensity between conditions.

D.5.5. Outcome.

At the conclusion of this analysis, we should have empirical data sufficient to recommend the epoch length and the control condition to successfully image the initial de-excitation substate of TM practice. Secondary outcomes include consistency of signal intensity for regions of interest within subjects, and variability across runs between subjects. Anatomically, based on previous research-driven neural models (see Sect. B.2.5.), we would expect to at least find cortical de-excitation with possible exceptions of medial and ventral prefrontal cortices, accompanied with some basal forebrain, basal ganglia and brainstem excitation, cerebellar de-excitation and no change in medial thalamic activity.

D.5.6. Conclusion of Aim 1 Experiment.

From this experiment, we expect to find four basic outcomes regarding brain mechanisms during meditation from an ABC-cycling protocol:

- (1) The epoch length that appears to best frame the de-excitation process;
- (2) The effects of two different control conditions;
- (3) The brain areas that appear most closely correlated with the de-excitation process, as measured by the ABC-cycling protocol; and
- (4) The intra- and intersubject variability of activation/deactivation patterns;

Collectively, these findings will help formulate a working model of brain mechanisms during the de-excitation substate of TM practice.

D.6. Examine the Patterns of Neural Activity during the Maximum De-Excitation Substate (Aim 2).

Experiment 2: Comparing BOLD patterns across periods of differing mental & blood-gas conditions

D.6.1. Hypotheses. We will test five hypotheses in this experiment.

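### The main effect of epoch length in D.5.4 pools TM with both controls and mixes areas expected to rise and fall, so it does not measure the best frame defined in D.5.2.1

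*Protocol*

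**What the plan says.** D.5.2.1 of the protocol defines what is sought: "The best frame will include maximum duration of the de-excitation process without the actual onset of a SBQ for most of the meditation epochs". This concerns meditation epochs only and is stated in terms of duration and SBQ onset.

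D.5.4 fixes the analysis. On the variate it says: "The Z-statistics for areas of significant fluctuations in signal intensity will be noted from all runs and used as the variate". On the model it says: "brain areas (4-8 estimate), and epoch condition (3) will be the factors, and the epoch-lengths (2) will be the repeated measure". The three conditions are TM, passive attending and mental counting.

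Item 3 of D.5.4 then expects a main effect for the repeated measure, "indicating the epoch length that best framed the initial de-excitation of TM practice". Item 4 expects an interaction between length and condition but does not tie it to the choice of length. D.5.5 says the experiment should allow a length to be recommended.

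Two places give expected directions by area. D.5.4 item 1 has "basal forebrain increases, slight cerebral and cerebellar cortex and mesencephalic reticular formation decreases, and no decreases in medial thalamus". D.5.5 expects cortical de-excitation with possible prefrontal exceptions, "accompanied with some basal forebrain, basal ganglia and brainstem excitation, cerebellar de-excitation and no change in medial thalamic activity".

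**The concern.** A main effect of length is, by construction, an average over every other factor in the model. Here that means all three conditions and all 4 to 8 areas. The definition in D.5.2.1 involves neither control, and neither SBQ onset nor frame duration enters the D.5.4 analysis.

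Two errors become possible. A length could be favoured because the controls give larger Z there. The plan's own reasoning makes this plausible, since item 4 expects shorter epochs to reduce variability whatever the condition. Conversely, a length that frames TM well could show no main effect because rises and falls offset one another.

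The best-framing epoch length is the first outcome listed in D.5.6, so the recommendation from Aim 1 is at stake.

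**Working it through.** **Plan's figures.** The protocol gives no error rate, effect size or power for the choice of length, so there is no figure to reproduce. The run layout in D.5.3 is consistent: 45 epochs x 30 s = 22.5 min, and two runs make 45 min.

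**Area directions.** My coding of D.5.4 item 1 is 1 up (basal forebrain), 3 down (cerebral cortex, cerebellar cortex, mesencephalic reticular formation) and 1 counted as zero (medial thalamus). For D.5.5 it is 3 up (basal forebrain, basal ganglia, brainstem), 2 down (cortex, cerebellum) and 1 zero (medial thalamus).

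**Shift in the main effect.** Let better framing add 1 unit of absolute Z in TM in every responding area, with the controls unchanged and equal weights.

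- Signed Z: shift = (areas up - areas down) / number of areas / 3 conditions.
- Absolute Z: shift = responding areas / number of areas / 3 conditions.

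| Area list | Signed Z | Absolute Z |
|---|---|---|
| D.5.4 item 1 | (1 - 3)/5/3 = -0.133 | 4/5/3 = +0.267 |
| D.5.5 | (3 - 2)/6/3 = +0.056 | 5/6/3 = +0.278 |
| Illustration, 2 up and 2 down | (2 - 2)/4/3 = 0 | 4/4/3 = +0.333 |

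With signed Z, the direction that means better framing reverses between the plan's own two lists.

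**Weight of the controls.** With absolute Z, let each control gain g at the worse-framed length while TM gains 1 at the better one. Per responding area the pooled difference is (1 - 2g)/3. It is zero at g = 0.5 and -0.333 at g = 1.

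**Contrast coding.** If each condition is instead contrasted with the mean of the other two, then (T - (A+B)/2) + (A - (T+B)/2) + (B - (T+A)/2) = 0. The pooled signed effect is then close to null by construction at either length.

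**Simulation.** The following are assumptions, not protocol figures: TM absolute Z of 6 at the better length and 5 at the worse; control Z of 4.5 in the same direction as TM; independent errors with SD 1 per cell; the higher mean Z wins; paired t-test at two-sided 0.05; 10,000 replicates. The 10 subjects are from D.5.3.

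- Signed Z, controls flat: wrong length chosen in 88% (item 1 list), 30% (D.5.5 list) and 50% (2 up, 2 down).
- Absolute Z, controls flat: wrong in 0.3 to 0.7%.
- Absolute Z, each control +0.5 at the worse length: wrong in about half of replicates.
- Absolute Z, each control +1.0 at the worse length: wrong in over 99%, and significantly so in 59 to 70%.
- TM-minus-controls contrast aligned to expected direction: wrong in about 0%. It was significant in the right direction in 90 to 95% with flat controls, and in 99.8 to 100% when the controls moved as above.

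**The case against.** The strongest reply is that item 3 is an expectation and not a formal decision rule. The same model has area as a factor, provides individual comparisons after main effects, and in item 4 looks at the length-by-condition interaction, which is close to the right quantity. All of that is true. Still, item 3 is the only analysis said to identify the best-framing length, and neither the comparisons nor the interaction is made the criterion.

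It is also fair that cancellation over areas needs signed Z, which the protocol implies by speaking of rises and falls but does not state. Under absolute Z with flat controls the pooled effect does well. The pooling over conditions remains either way.

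Three stronger readings are tempting, and the documents do not support them.

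- A reader might infer that the longer epoch wins merely by having more scans. D.5.3 gives about 22 min per run for both lengths; the count "including 45 total epochs, 15 epochs each condition" belongs to its 30 s example. In a design simulation at about 22 min per run (TR 2.2 s, white noise, same true signal), the ratio of Z at 40 s to Z at 20 s was 1.02.
- A reader might infer that the Z criterion rewards epochs that capture SBQ. This is not shown. The global signal increase in D.6.2.1 is reported for breath-holding, and it would oppose the decreases predicted in D.5.4 and D.5.5. D.2.2 enters respiration as a covariable, and D.6.2.1 expects only a small respiratory effect during SBQ.
- A reader might infer that D.5.2.1 and Hypothesis 1 always conflict. B.2.4.2 and D.5.2.1 centre the two lengths on a screening estimate of the time to SBQ. If the longer length passes that time, both favour the shorter. They conflict only when both lengths are free of SBQ in most epochs.

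**Conclusion.** The point holds in this narrow form: the pooled main effect of length does not measure the best frame that D.5.2.1 defines. TM has one third of the weight whether Z is signed or absolute. With signed Z, the same improvement in framing moves the effect by -0.133 or +0.056 depending on which of the plan's two area lists applies.

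These shifts rest on equal weighting, my coding of the lists, and an equal gain in every responding area. The simulated error rates show that a wrong choice is possible; they do not estimate how likely it is in this study. For an exploratory experiment this should be corrected in the analysis text. It does not undermine the design or the data collection.

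**What to change.** In D.5.4 item 3 and D.5.5:

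1. Remove the statement that the pooled main effect of length indicates the best frame.
2. Base the imaging comparison of lengths on the TM-minus-control contrast at each length, that is, the interaction already in item 4. Take it within area and align it to each area's pre-stated direction. This needs one agreed list: item 1 expects a mesencephalic decrease, whereas D.5.5 expects some brainstem excitation.
3. Report for each length the share of TM epochs with SBQ onset, from the respiration trace that D.2.2 already records. In line with D.5.2.1, do not recommend a length with SBQ onset in most TM epochs. The contrast in step 2 cannot supply this, because it does not measure SBQ-free duration.
4. Reconcile the preference in D.5.2.1 for the longest frame with the preference in Hypothesis 1 for the shorter epoch, for the case where both lengths are SBQ-free.

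The cost is minor analysis wording and a count from existing data, with no extra scanning.

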Research on a various forms of respiratory challenge, e.g., CO₂ inhalation, hyperventilation, breath-holding, etc., versus normal breathing have reported reproducible networks of forebrain and brainstem activation based on significant and specific changes in BOLD signal intensity. Furthermore, these patterns are discernible even with the considerable confounds of respiratory-induced variability of head and brainstem position, as well as wide variations in blood gas values. In contrast, the spontaneous breath-quietness periods during the TM practice occur under relaxed, non-stressful conditions, with the onset, persistence and offset of spontaneous breath-quietness not dependent upon volitional or intentional control or even awareness of the individual. Because of the restful state of the meditator, there is also minimal head movement artifact. **In conclusion, we anticipate that the potentially small, independent effects of respiratory-mediated BOLD signal changes will not significantly confound the data collected during spontaneous breath-quietness substate of the TM technique.**

D.6.2.2 Effectsof cessation of mechanical respiratory activity. Intentional breath-holding will be used to clarify the impact of breath-quietness on brain function and MRI signal intensity. These breath-holding periods will allow comparison of CO₂ variation and control for effects arising from cessation of mechanical respiratory activity. Because breath-quietness occurs spontaneously during TM practice, the cycling protocol cannot be used requiring the recording of images during a “self-paced” protocol, in which no instructions are given and TM is uninterrupted. This non-cycling design will produce a 5 min time-series of scans that will have reoccurring periods of spontaneous breath-quietness embedded in it. In addition, analytical approaches will be used that are capable of marking desired scans and comparing the variability of signal intensity in the time series. Event-related and state-related fMRI methodologies will be used to analyze the continuous sequence of scans [personal communication, [name] and [name], 2001][[name], 1998 #4780;[name], 1998 #4781;McCarthy, 1999 #5209;Schacter, 1997 #5391].

The BOLD signal and physiological measures will be collected during four runs of 12 minutes duration each. Each 12 min run comprises three periods: 5 min uninterrupted meditation, 5 min structured breath-holding, and 2 mins non-task, eyes-closed (EC) control. The meditation period are free running with no interruptions from experimenters. During the meditation period we expect 3-5 SBQ periods. The breath-holding periods are structured by duplicating the previous SBQ pattern by voice command from experimenter, the onset and offset of IBH corresponding to SBQs time frame for each subject. The non-task control period will be determined from the outcome of experiment 1 (Aim 1), and either be passive-attending or mental-counting. The physiological measures will include respiration and transcutaneous CO₂ measurements. Four runs will take 48 minutes, or about 1 hr due to 30 rest periods between conditions. Therefore, each fMRI session will last about 90 minutes per subject.

D.6.4. Event-related fMRI analysis (Hypotheses 1-3).

Er-fMRI methodologies will be used to probe brain mechanisms during the onset of two conditions, during SBQ and IBH periods. The scans will be aligned relative to the onset of either SBQ or IBH during the four runs to permit signal averaging: 4 images before (12 secs) and 4 images after onset (12 secs). A TM meditator, selected in our screening protocol, may exhibit 25-30 spontaneous breath-quiet periods in a 30-min TM session [9, 20-22]. We estimate 12-20 periods will occur in our four meditation periods.

Images from individual runs will first be normalized to correct for the range of intra- and inter-subject signal intensity and temporal drift [171]. Specifically, normalization will involve: (1) scaling of signal intensity to a fixed value of 1000; (2) linear slope removal in a voxel-by-voxel basis; (3) spatial filtering with a one-voxel radius Hanning filter, and; (4) removal of the mean signal intensity on a voxel-by-voxel basis. The normalized fMRI images will then be aligned relative to the onset either SBQ or IBH periods. These images will be averaged within each subject. The mean image for each subject will be transformed into stereotaxic atlas space [208] using the highest point of the mid-sagittal plane and the anterior and posterior commissures. The atlas-transformed matrices will then be averaged across subjects.

Statistical parameter maps will be constructed using sets of pre-constructed hemodynamic curves. Cohen's hemodynamic model, often used in fMRI experimental analysis, was derived from stimulation of the visual cortex [170]. Hence, there is no reason to suspect it is the best response function to apply to this task (meditation) or to other brain areas (subcortical nuclei). Therefore, new response models will be constructed by systematically varying, initially, the onset delay (lags) of Cohen's standard hemodynamic response model. Other parameters besides onset could also be varied, e.g., shape of curve. Sequential application of each model will display the inherent temporal and spatial dynamics of the hemodynamic response to the onset of the spontaneous breath-quiet substate. Each model will generate a different map of the brain dynamics. For example, short versus mid or long lags could be reasonably expected to produce different anatomical patterns [171]. On the other hand, the brain pattern may remain similar, but the signal intensity of each brain area may vary. Models derived from both conditions can be compared to determine statistical significance of the two brain states. Specifically, we will use MANOVA to compare onset, latency and peak signal intensity for different ROIs for the two conditions. We expect, in general, that the statistical parameter maps for intentional breath-holding will depict a diffuse, non-localized distribution of activation in contrast to localized patterns of activation during spontaneous breath-quiet. Hypothesis 1 & 2 will use a correlational analysis to test association between er-fMRI BOLD signal intensity and blood gas levels.

D.6.4.1 Blood Gases and IBH. O₂ and CO₂ levels will be correlated with er-fMRI BOLD signal intensity during the 6 scans (18 s) preceding and the 4 scans (12 s) following the onset of IBH. Data will be analyzed with a Pearson correlation to help distinguish blood gas-dependent vs. neural-dependent BOLD changes.

- We expect significant correlations between CO₂, but not O₂, with BOLD signal during IBH.

D.6.4.2. Blood Gases and SBQ. O₂ and CO₂ levels will be correlated with er-fMRI BOLD signal intensity during the 6 scans (18 s) preceding and the 4 scans (12 s) following the onset of spontaneous breath-quiet. Data will be analyzed with a Pearson correlation help distinguish blood gas-dependent versus neural-dependent BOLD changes.

- We expect minor blood gas changes and hence, few significant correlations between CO₂, with BOLD signal during spontaneous breath-quietness.

D.6.4.3. Neuroimages during SBQ and IBH. Er-fMRI will be compared between IBH and SBQ periods, using a repeated measures MANOVA.

- We expect main effects for brain areas. Animal hypercapnia [209] and human breath-holding [157, 203, 210, 211] studies indicate that hypercapnic conditions are associated with global increases in most cortical and subcortical grey matter blood flow. Thus, we expect region-independent, nonspecific activation in all areas during IBH. In contrast, we expect region-dependent, specific activation or deactivation of BOLD signal intensity during SBQ.
- We expect main effects for the repeated measures, indicating significant differences in signal intensity across time.
- We expect no significant interactions.

D.6.5. State-related fMRI analysis (Hypotheses 4-5).

Sr-fMRI methodologies will be used to probe brain mechanisms during SBQ, IBH, and control periods. In the previous three analyses, we identified brain areas that displayed significant time-locked relation to the onset of both IBH and SBQ. A complementary approach to identification of brainstate changes is the use of state-related methodology. This method divides the time-series into condition-specific bins for comparison. Scans collected in Expt. 2 will be categorized into six bins: before and during either IBH, SBQ or equal-length periods during eyes-close (EC) control. Scans assigned to each bin will be compared by multiple linear regression, correcting for differences in blood gas levels across the three conditions.

D.6.5.1. Sequence of Analysis. First, we will create a dummy time-series of 1, or 2's that correspond to the scans before and during three conditions: IBH, SBQ or EC. The dummy time-series then will be convolved with the hemodynamic response model using the Cohen Model. This will yield the dummy independent variable that will be entered into the multiple linear regression analysis along with O₂ and CO₂ data. The scans for each of the periods will be dependent variables in the analysis. We will examine the resulting statistical parameter maps for clusters of pixels displaying significant fluctuations in signal intensity. The Z-statistic of the activated clusters that meet our criteria (D.2.3.) will be entered as variates in a repeated-measures ANOVA, with brain area as the factor and the period as the repeated measures.

D.6.5.2. Comparison between conditions: SBQ, IBH and EC. Condition differences will be assessed with two-way repeated measures ANOVA with brain areas and condition as factors, and the two periods (before and during the conditions) as the repeated measures. Individual comparison will be conducted if there are significant main effects.

- We expect no main effects for brain areas, indicating highly variable activation across brain areas yielding no consistent relations.
- We expect main effects for condition (SBQ, IBH, EC), indicating different brain mechanisms are active during each condition. For example, during IBH we expect higher levels of task effort and motor system activation, and possibly higher CO₂ levels to yield the predicted main effect.
- We expect main effects for the repeated measure (before and during). The 'before' periods may be somewhat similar, while the 'during' periods may be significantly different.
- We expect significant interactions, indicating differential involvement of some brain areas during the three conditions. For instance, the cerebral cortex may exhibit lower BOLD signal in both 'before' periods. However, the cortex is expected to be activated during IBH, while remaining low or reduced during SBQ.

D.6.6. Outcome. This experiment will help identify:

- (1) Neural mechanisms specific to the generation and maintenance of IBH, and the effects of hypercapnia and loss of mechanical respiratory activity on BOLD signal intensity.
- (2) Neural mechanisms specific to SBQ periods, as compared to a variety of brainstates, including, other meditation periods, IBH, and EC.

D.7. Conclusion of Research Design and Methods.

These data should help elucidate the spatiotemporal structure of neurophysiological processes during the practice of TM. Previous EEG and autonomic research have provided a rough map of the possible brain mechanisms underlying distinct substates of meditation [7-9, 22]. Data obtained from this R21 neuroimaging research should provide a more reliable and accurate model of brain mechanisms underlying TM practice. The proposed research will provide: (1) a tested fMRI protocol for imaging meditation experience; (2) a determination of signal sources during two principal substates of TM practice; and (3) key experimental protocol and analysis issues to yield successful comparative studies of meditation. The systematic substate characterization resulting from this grant will enable researchers to generalize the research methodology and mechanisms to the investigation of other meditation techniques, and thereby, facilitate relatively rapid progress in employing the new field of neuroimaging to examine brain dynamics of meditation. Progress in understanding brain dynamics of meditation and other CAM techniques will depend upon such careful substate research.

G. LITERATURE CITED

1. Eisenberg, D.M., et al., *Trends in alternative medicine use in the United States, 1990-1997: results of a follow-up national survey*. *Jama*, 1998. 280(18): p. 1569-75.
2. Eisenberg, D., et al., *Unconventional medicine in the United States: Prevalence, costs, and patterns of use*. *The New England Journal of Medicine*, 1993. 328(4): p. 246-252.
3. Roth, R., *The Transcendental Meditation Program*. 1994, New York: Primus Publishing, Inc.
4. Chalmers, R., et al., eds. *Scientific Research on the Transcendental Meditation program: Collected Papers (Vol. 2-4)*. 1990, MVU Press: Vlodrop, The Netherlands.
5. Orme-Johnson, D.W. and J. Farrow, eds. *Scientific Research on the Transcendental Meditation program: Collected Papers (Vol. 1)*. 1977, MERU Press: Rheinweiler, West Germany.
6. Wallace, R.K., D.W. Orme-Johnson, and M.C. Dillbeck, eds. *Scientific Research on the Transcendental Meditation Program: Collected Papers, Vol. 5*. 1990, MIU Press: Fairfield, Iowa.
7. [name], A.T., *Brain state and attentional mechanisms in the transition to a de-excited state of consciousness: A neuro-psychological model of transcending*. *Soc. Neurosci. Abst.*, 1986. 16: p. 1446.

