The sequence of analysis includes: (1) discarding the initial three scans of each run due to magnetic instability; (2) correcting for movement artifacts by the co-registration of the time series using AIR (automatic image registration); (3) morphing the distorted fMRI image onto the accurate, high resolution MRI anatomic image, by registering fMRI images to the 8-shot EPI scan using AIR and registering the T1-slice to the 3D-volume using image intensity; (4) generation of statistical parameter maps from the *t*-statistics resulting from the multiple linear regression—a statistical parameter map (SPM) is a map of all pixel areas that exceed a specified statistical threshold and; (5) transforming the *t*-statistic maps into *Z*-statistic maps for statistical analysis. With large numbers—100 or more—the *t*-distribution approximates a *Z*-distribution [184]. These final statistical parameter maps will reflect significant fluctuations in signal intensity during the two conditions of the cycling tasks, after the contribution of other physiological variables have been statistically removed.

D.2.3. Statistical analysis.

One of the valuable characteristics of fMRI is that the relatively high signal to noise ratio allows detection of significant changes in signal intensity *within* a single subject [185]. The steps for statistical analysis of all data will include:

- (1) The SPM [184] for the runs in each condition will be examined. Areas of significant signal fluctuations will be determined using two criteria [92]: (a) the *Z*-statistic > 4.0, ($p < 10^{-7}$), and (b) the cluster must contain a minimum of four pixels that touch on the sides or corners (eight-neighborhood connectivity).
- (2) We will examine the first run for possible adaptation effects. If the first run differs significantly from subsequent runs, we will consider excluding the first run from the overall analysis.
- (3) The *Z*-statistic of significant areas of fluctuations in signal intensity are noted when they meet the criteria above and are in 2 of the 3 statistical parameter maps from multiple runs in the same condition.
- (4) These *Z*-statistics will be used in parametric analyses.

D.2.4. Sample size.

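### Read in the order written, the event-related maps rest on 8 averaged images (about 6 residual df), where the plan's 100-or-more basis for reading t as Z > 4.0 does not hold

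*Protocol*

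**What the plan says.** D.2.2 turns the t-maps from the multiple regression into Z-maps and gives one ground for it: "With large numbers—100 or more—the *t*-distribution approximates a *Z*-distribution". D.2.3 opens with "The steps for statistical analysis of all data will include", so its rules reach the event-related maps by default. They are a Z-statistic above 4.0, a cluster of at least four touching pixels, and appearance of the area in 2 of 3 maps from repeated runs of a condition.

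D.6.4 aligns the scans of the four runs to onset "to permit signal averaging: 4 images before (12 secs) and 4 images after onset (12 secs"). After normalization and alignment come two averaging steps: "These images will be averaged within each subject", and, after transformation to atlas space, "The atlas-transformed matrices will then be averaged across subjects". The next step in the text is: "Statistical parameter maps will be constructed using sets of pre-constructed hemodynamic curves". The curves are the standard response model shifted by a series of lags.

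No section states how many images enter that fit, how many df remain, or how t is converted to Z for these maps. D.6.2.2, introducing both methods, says that they analyze the unbroken series of scans.

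**The concern.** Averaging over events lowers the noise in each of the 8 images but does not add points to the fitted series. Residual df depend on the number of points fitted, so 12 or 20 averaged events leave the same df as one. The large-number argument suits a 22-minute cycling run in Experiment 1. It does not suit an 8-point series. This is separate from serial correlation and from the loss of between-subject variance: it would hold with independent scans and for one subject's averaged series.

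D.6.5 says that the event-related analyses identify areas time-locked to onset, and D.6.4 compares regions between the two conditions by MANOVA for the SBQ-IBH hypothesis (D.6.1.3). The choice of fit and conversion can therefore change which areas are reported as active.

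**Working it through.** **Inputs**
- Points in the averaged series: 4 + 4 = 8 (D.6.4).
- Model: mean plus one curve, 2 parameters (assumed; D.6.4 does not say).
- Threshold: Z > 4.0 with four touching pixels (D.2.3). Large-number basis: 100 or more (D.2.2).
- Grid 64 x 64 with 19 slices, TR 2.2 s (D.2.1).
- Four runs, each with 5 min of meditation and 5 min of breath-holding (D.6.3). 12 to 20 SBQ periods over the four meditation periods (D.6.4).

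**1. The plan's own figure.** D.2.3 equates Z > 4.0 with p below 10^-7. This does not reproduce: P(Z > 4) = 3.17 x 10^-5 one-sided, or 6.33 x 10^-5 two-sided. A p of 10^-7 needs Z of about 5.20 (one-sided) or 5.33 (two-sided). That is a separate error; the comparisons below use 3.17 x 10^-5.

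**2. Residual df on the 8-point reading.** 8 - 2 = 6.

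**3. If t is read as Z.** P(t > 4) at 6 df = 0.00356. Ratio: 0.00356 / 0.0000317 = 112. The ratio is the same one- or two-sided, and is larger with fewer df.

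**4. If t is converted exactly.** t = 4 at 6 df becomes Z = 2.69 and fails the threshold. To reach Z = 4, t must exceed 9.84.

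**5. Null pixels above 4.** Whole grid: 64 x 64 x 19 = 77,824 pixels. 77,824 x 0.00356 = 277, against 77,824 x 0.0000317 = 2.5 for a true Z. If brain fills a quarter of each slice (assumed): 19,456 pixels, giving 69 against 0.6.

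**6. With the four-pixel rule.** Simulated null volumes used 8 images, one step regressor, temporally independent noise and an assumed 3 x 3 kernel for the planned one-voxel Hanning filter.
- 6 df, quarter-slice brain: 42% to 45% of maps had at least one false cluster.
- 6 df, all pixels including air: 88% to 93%.
- True Z maps, all pixels: 0.2% to 0.6%.
- No spatial correlation: the cluster rule removed all false clusters.

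These figures are for one curve. The extra looks from fitting several lags are not counted.

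**7. With the 2-of-3-maps rule.** When clusters had to overlap in 2 of 3 independent null maps, 0 of 100 sets kept a false cluster, with or without the brain mask.

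**8. Other readings of D.6.4** (independent errors assumed).
- Unaveraged event images: 12 x 8 = 96 to 20 x 8 = 160 images, so 94 to 158 df, and a ratio of 2.0 to 1.5.
- Continuous series: 4 x 300 s / 2.2 s = 545 scans per condition, and a ratio of about 1.14.

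**The case against.** The strongest reply is that the 8-point fit is inferred from the order of the steps. D.6.2.2 points to the continuous series, and D.2.2 uses physiological time series as real-time covariables, which suits a scan-by-scan regression. On those readings the inflation is at most about twofold. This stands as a reason for moderate confidence. It does not remove the point: D.6.2.2 is a general introduction to both methods, D.6.4 is the procedure to be followed, and its sequence puts averaging before the maps.

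Second, D.2.2 speaks of transforming t-maps, not of relabelling them, and a probability-preserving transform would hold the error rate. That is correct, and conversion detail may properly sit in an SAP. But the only justification given is the large-number one, and at 6 df the exact route sets a bar of t > 9.8.

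Third, the 2-of-3-maps rule also applies to all data and removes the false clusters. It does where it can be used. D.6.4 pools the four runs into one average per subject before mapping, so there are no per-run maps for it to compare.

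Fourth, a reader might add O2 and CO2 as covariables and infer 4 df, a 255-fold excess and a needed t of 17.4. The documents do not support this for D.6.4, which handles blood gases by Pearson correlation; regression on O2 and CO2 is specified for the state-related analysis in D.6.5.

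**Conclusion.** The point holds conditionally. Followed in the order written, D.6.4 leaves about 6 residual df, and the stated basis for Z > 4.0 fails. Reading t as Z gives about 112 times the nominal tail probability; an exact conversion requires t > 9.8 and would miss real responses. Neither is the rule that the plan describes.

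The cluster consequence is about 45% of brain-sized null maps, given independent temporal noise, the assumed kernel and a quarter-slice brain. A reader might infer from the whole-grid figures that a null map will usually show activation. Those figures count air outside the brain, and the result depends on the assumed spatial correlation. Nor do the documents show an established 112-fold error rate, because they state neither the df nor the conversion. It would also go too far to say that these maps alone define the regions for the SBQ-IBH hypothesis: D.6.1.3 names the anterior cingulate cortex and brainstem in advance.

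Should-fix, moderate confidence.

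**What to change.** In D.6.4:
- Fit the lagged curves to each subject's unaveraged scans, with SBQ or IBH onsets as events. That gives about 545 scans per condition over four runs, or 300 / 2.2 = 136 per run, both above the plan's own 100.
- Make maps per run so that the 2-of-3 rule can operate, and say how it carries over to four runs.
- Keep the 8-image averages for display.

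In D.2.2, convert t to Z through the exact p-value at the residual df, and state those df. While editing, reconcile the timing: 4 images in 12 s implies a TR of 3 s, against the 2.2 s in D.2.1.

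The cost is analysis wording and slightly more computing. The same scans are used. The change should be made before the Experiment 2 data are analyzed.
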